4.5 Justification of Exclusions of Pregnant Women and Children

4.5.1 Exclusion of Pregnant and Breastfeeding Women

Pregnant women are excluded from this study because the effects of SAB-176 on the developing human fetus are unknown with the potential for teratogenic or abortifacient effects. Because there is an unknown but potential risk for adverse events (AEs) in nursing infants secondary to treatment of the mother with SAB-176, women that are breastfeeding will also be excluded from the study.

4.5.2 Exclusion of Children

Because there are insufficient data regarding dosing or AEs events available in adults to judge the potential risk in children, children are excluded from this study.

4.6 Subject Withdrawal

Subjects (or their legal surrogates if subjects become unable to make informed decisions) can terminate study participation at any time without prejudice. If a subject terminates participation before completing the study, the reason for this decision will be recorded in the study record.

Best efforts will be made to follow withdrawn subjects who have received study drug administration for safety. Subjects who withdraw from the study after study drug administration will not be replaced.

4.7 Discontinuation of Subject by Investigator

The Investigator has the right to withdraw subjects from the study. Subjects may be withdrawn from the study for any of the following reasons:

- The subject is lost to follow-up.
- The Investigator believes that continuation in the study would be detrimental to the subject. In general, subjects withdrawn for AEs will still be followed for safety follow-up if possible.
- If, in the Investigator's best judgment, discontinuation is in the subject's best interest.

The reason for withdrawal from the study is to be recorded in the study record. All subjects should be followed for safety assessments. If a non-serious AE is unresolved at the time of discontinuation, efforts should be made to follow up until the event resolves or stabilizes, the subject is lost to follow-up, or there is some other resolution of the event. The Investigator should make every attempt to follow all serious adverse events (SAEs) to resolution.

Subjects withdrawn from the study after study drug administration will not be replaced.

4.8 Discontinuation of Study

SAB Biotherapeutics as the study sponsor, the study site IRB, and the Food and Drug Administration (FDA) may terminate this study at any time. Reasons for terminating the study may include, but are not limited to, the following:

- The incidence or severity of an AE in this or other studies indicates a potential health hazard to subjects.
- If there is one death, irrespective of attribution by the investigator/medical monitor. Subject enrollment is unsatisfactory.
- Data recording is inaccurate or incomplete.
- Investigators do not adhere to the protocol or applicable regulatory guidelines in conducting the study.

4.9 Emergency Unblinding

If a subject experiences a SAE, and the treating clinician requests unblinding of the study treatment, the Principal Investigator (PI) or designee will be contacted. If the PI or designee is in agreement that unblinding is necessary, the PI or designee will contact the PPD Phase 1 Clinic Pharmacy for release of the randomization code for the subject to the treating clinician. For individual subject unblinding, the site will follow their unblinding procedures per SOP-AUSCLN-506. The sponsor and Medical Monitor will be informed within one business day that unblinding was necessary. In this case, the subject is still considered enrolled in the study, and the data is still used for analysis.

5 TREATMENT

5.1 Randomization and Blinding

The randomization schedule will be generated using SAS Version 9.4 or later (SAS Institute Inc, Cary, North Carolina), which will link sequential volunteer randomization numbers to treatment codes. The randomization schedule and the volunteer-specific emergency unblinding documentation will be provided to the unblinded pharmacist(s) at the clinic site.

Study participants and study team (PI and associate Investigators and study staff) will be blinded throughout the entire study. The study team will be unblinded after the Study Day 90 visit, all laboratory (and immunogenicity) results are available, and the final monitoring visits has occurred.

The infusion will be provided in an opaque bag to obscure the bag, since SAB-176 may develop bubbles similar to what is seen with IVIg, if the product is agitated. This process has been used in other studies (INSIGHT influenza IVIG) and was successful in maintaining blinding of the study team.

5.2 Formulation, Packaging and Labeling

5.2.1 SAB-176

SAB-176 is a purified human immunoglobulin G (hIgG) designed to specifically bind to Type A and Type B influenza viruses. The product is in development for use as a therapeutic agent to treat patients who are infected with Type A and Type B influenza viruses. The hIgG is purified from the plasma of immunized transchromosomal (Tc) bovines that were immunized with a quadrivalent recombinant hemagglutinin (HA) protein vaccine produced in insect cells.

The product is in a sterile liquid form formulated in 10 mM glutamic acid monosodium salt, 262 mM D-sorbitol, 0.05 mg/mL Tween 80, pH 5.5. The drug product will be administered intravenously and will be diluted in saline per the clinical protocol.

5.2.1.1 Label

SAB-176 anti-Influenza
Human Immunoglobulin Intravenous (Tc Bovine-Derived)
70.12mg/ml (701.2mg in 10mL) For Intravenous Use Only
Lot No: PD2001010QR Manufacture Date: 03 Feb 2020
Store at 2-8°C
Mfr: SAB Biotherapeutics, Inc. Sioux Falls, South Dakota, USA
Caution: New Drug--Limited by Federal law
to investigational use.

Figure 1: SAB-176 Vial Label

5.2.1.2 Storage

Store SAB-176 at 2-8°C

5.2.2 Saline Control

Subjects randomized to the control infusion will receive normal (0.9%) saline in approximately the same volume as they would have received if randomized to the active arm.

5.3 Dosing and Administration

The NIH clinical center guidelines for administration of a standard human 10% IVIg (10g/100mL) are for the initial rate to be 0.6 mL/kg/hr, and the rate can be increased gradually to a maximum of 4.8 mL/kg/hr, if tolerated.

SAB-176 will be prepared in the following dilutions:

- Cohort 1 will be prepared as a solution 1mg/1ml (0.1% solution by weight), which is 1/100th the concentration of standard human IVIg (e.g. Gammunex).
- Cohort 2 will be prepared as a solution 4mg/1ml (0.4% solution by weight), which is 1/25th the concentration of standard human IVIg.
- Cohorts 3&4 will be prepared as a solution 20mg/1ml (2% solution by weight), which is 1/5th the concentration of standard human IVIg.

The dose of study drug will be calculated based on the subject's dose cohort and weight (up to a maximum weight of 100 kg). The pharmacy will prepare a bag containing the dose of SAB-176 plus as much normal (0.9%) saline as is needed to reach the above listed concentrations. The infusion will be provided in an opaque bag to obscure the bag (as the SAB-176 may develop

bubbles like IVIg if agitated). The drip chamber will also be covered, but accessible if needed by nursing staff for verification of flow rate, etc.

Table 3: Dosing and Administration

Cohort	Dose (mg/kg)	Concentration	Start Rate (mL/kg/hr)	End Rate (mL/kg/hr)	Start Rate (mg/kg/hr)	End Rate (mg/kg/hr)	Proportion of Human IVIG Rate	Duration (mins) (approx.)
1	1	1 mg/mL (0.1%)	0.5	2	0.5	2	1/120 th – 1/240 th	53
2	10	4 mg/mL (0.4 %)	0.5	3	2	12	1/30 th - 1/40 th	85
3	25	20 mg/mL (2 %)	0.5	1	10	20	1/6 th - 1/12 th	83
4	50	20 mg/mL (2 %)	0.5	2	10	40	1/6 th - 1/10 th	97

The infusion will be started at of 0.5 mL/kg/hr, escalating by 0.5 mL/kg/hr increments every 15 minutes to a maximum specified above (end rate).

It is anticipated that the infusion is prepared the morning of the infusion. Since the study drug has been shown stable for 24 hours when mixed in saline, the infusion should be started within 6 hours of preparation in order to assure completion within normal working hours.

The dosing of an individual subject will be slowed and or stopped (depending on clinical assessment) for the following:

- hypotension (systolic or mean blood pressure decreases by 20 mmHg)
- shortness of breath, wheezing, or desaturation
- pain, tenderness, erythema, or swelling around the infusion site
- fevers, chills
- Other adverse reactions not specified, that are concerning for infusion related adverse events

After clinical assessment, and resolution or improvement of the event of concern, the infusion may be resumed. If the event is not resolving in a reasonable amount of time, the infusion will not be resumed.

However, in order to establish absolute criteria for stopping an infusion – the treatment should be immediately stopped should any of the following occur:

- Profound hypotension (systolic blood pressure < 85 mmHg)
- Shortness of breath, wheezing, or sustained (i.e., ≥ 10 seconds) oxygen saturation < 92% on room air
- Severe (Grade ≥ 3) local infusion site reactions, including pain, tenderness, erythema, or swelling as defined in the protocol-specified toxicity grading scale
- Body core temperature exceeding 38.5°C
- Suspected sepsis
- Severe chest pain
- Suspected anaphylaxis

The subject's actual time of drug administration will be recorded in the source documents.

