There is the risk of off-target binding of the IVIg. In the worst case, this could cause immune activation (cytokine storm). The tissue cross reactivity assays do not predict any off-target binding, and this has not been seen in any other animal IVIg (of Fab fragment) preparations, so this risk is considered low.

For Horse Heptavalent Botulism Antitoxin, the most common adverse reactions in all healthy subjects were headache (9%), pruritus (5%), nausea (5%), and urticaria (5%). Other adverse reactions reported in less than 4% of subjects included pyrexia and throat discomfort. All reported adverse reactions were considered mild or moderate. No serious adverse reactions were reported. Two moderate acute allergic reactions that required premature termination of the infusion and treatment were reported. Reactions were predefined as mild if the subject was aware but could tolerate the symptoms. Moderate reactions were predefined as discomfort enough to interfere with normal daily activity.

The development of antibodies to bovine proteins and potential for food allergies is a theoretical concern. There is precedent for animal antibodies (or Fab fragments) being obtained from animal plasma and given to humans.

- Rabbit Anti-thymocyte Globulin [Thymoglobulin]
(<http://products.sanofi.ca/en/thymoglobulin.pdf>)
- Horse Anti-thymocyte Globulin [Atgam]
(<http://www.fda.gov/downloads/BiologicsBloodVaccines/BloodBloodProducts/ApprovedProducts/LicensedProductsBLAs/FractionatedPlasmaProducts/UCM199603.pdf>)
- Horse Heptavalent Botulism Antitoxin
(<http://www.fda.gov/downloads/BiologicsBloodVaccines/BloodBloodProducts/ApprovedProducts/LicensedProductsBLAs/FractionatedPlasmaProducts/UCM345147.pdf>)
- Sheep Digoxin Immune Fab [DigiFab]
(<http://www.fda.gov/downloads/BiologicsBloodVaccines/BloodBloodProducts/ApprovedProducts/LicensedProductsBLAs/FractionatedPlasmaProducts/ucm117626.pdf>)

- Sheep Digoxin Immune Fab [DigiBind]
(<http://dailymed.nlm.nih.gov/dailymed/archives/fdaDrugInfo.cfm?archiveid=19044>)
- Sheep Crotalidae Polyvalent Immune Fab [CroFab]
(http://www.crofab.com/documents/CroFab-Prescribing_Information.pdf)

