Upon review of these package inserts, the development of anti-drug antibodies was noted only in Horse Heptavalent Botulism Antitoxin (11 of 271 subjects). There was no warning in any of these products concerning the development of allergies to other animal proteins, nor of any food allergies. As SAB-176 is a transgenic human IgG, the risk should be even further minimized. However, given the American diet is often heavy in bovine products (milk and/or beef, including derivatives), there is the risk of development of anti-bovine antibodies that is stimulated with repeated exposure. Given the data above and the lack of precedent for the development of food allergies after exposure to similar products, it is anticipated this risk with SAB-176 is very small.

Patients exposed to topical bovine thrombin products (previously used in surgical procedures e.g. fibrin glue) have developed antibodies towards bovine thrombin and contaminating bovine factor V; these antibodies can cross react with human clotting factors and may cause coagulopathy (7). In that series, postoperative coagulation abnormalities were more common in patients with antibodies to human coagulation proteins. SAB-176 clinical lots contain less than 5 ppm (parts per million) of bovine plasma proteins, but the clinical significance of this level of bovine contaminants is not known. Regardless, the serial assessment of PT/PTT in the study will monitor for any coagulation abnormalities in the subjects receiving SAB-176.

As SAB-176 is bovine derived, it may contain galactose-alpha-1,3-galactose (alpha-Gal) glycosylation of the IgG. In other products, the alpha-Gal glycosylation has been shown to be the source of immune based hypersensitivity reactions. For example, the epidermal growth factor receptor (EGFR) inhibitor cetuximab is a monoclonal antibody with alpha-Gal glycosylation. Cetuximab, while a marketed product, has been associated with hypersensitivity reactions, including anaphylaxis. In most subjects that had hypersensitivity reaction to cetuximab, IgE antibodies were present in pretreatment samples (8). This study is designed to start with very small doses, with close monitoring for similar hypersensitivity reactions.

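### Protocol 5.3 puts ungraded shortness of breath and wheezing in both the discretionary and the absolute stopping lists, and does not say whether an absolute stop is final

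*Protocol*

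**What the plan says.** Section 5.3 (Dosing and Administration) opens the first list with "The dosing of an individual subject will be slowed and or stopped (depending on clinical assessment) for the following". The respiratory entry in that list is "shortness of breath, wheezing, or desaturation", with no grade or threshold. The list is followed by a resumption rule: "After clinical assessment, and resolution or improvement of the event of concern, the infusion may be resumed". The only stated bar to resumption is an event that fails to resolve within a reasonable time.

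The second list begins "However, in order to establish absolute criteria for stopping an infusion" and requires treatment to stop at once. Its respiratory entry begins "Shortness of breath, wheezing, or sustained" and goes on to an oxygen saturation below 92% on room air lasting at least 10 seconds. The duration and the 92% limit qualify saturation only, so shortness of breath and wheezing are ungraded here too. Suspected anaphylaxis is a separate entry in this second list.

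Section 11.6 allows the subject, the investigator or the sponsor to end an infusion at any time. For the slowing and stopping criteria it refers back to 5.3.

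**The concern.** Nurses and physicians apply this rule in real time. For one and the same sign, one list lets them slow the infusion and carry on, while the other tells them to stop. Wheeze or breathlessness during an infusion can be an early sign of hypersensitivity, a hazard that the protocol itself brings forward. Section 8.1.1 notes that SAB-176 may carry alpha-Gal, and relies on very small starting doses "with close monitoring for similar hypersensitivity reactions". For the horse antitoxin that 8.1.1 treats as the most similar product, it records: "Two moderate acute allergic reactions that required premature termination of the infusion and treatment were reported".

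At stake is the handling of an individual subject who wheezes, improves, and could then be given the rest of the dose because the text does not settle the matter. Staff could also handle the same sign differently from one subject to the next.

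**Working it through.** The point itself needs no calculation. It rests on comparing the two lists in 5.3 sign by sign.

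| Sign in both lists | Discretionary list | Absolute list | Separated? |
|---|---|---|---|
| Blood pressure | fall of 20 mmHg, systolic or mean | systolic below 85 mmHg | yes |
| Oxygen saturation | any desaturation | below 92% on room air for 10 seconds or more | yes |
| Infusion site | any listed local reaction | Grade 3 or higher | yes |
| Temperature | fever | core temperature above 38.5°C | yes |
| Shortness of breath | ungraded | ungraded | no |
| Wheezing | ungraded | ungraded | no |

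Four of six signs step up between the lists and two do not. The section is evidently built as two tiers, and these two signs sit in both with nothing to tell the tiers apart.

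Next, which instruction governs? The order in 5.3 is: discretionary list, resumption sentences, then the contrast "However, in order to establish absolute criteria for stopping an infusion", then the absolute list. Read in sequence, the resumption sentences belong to the first list, and the absolute list is set against them. So the immediate stop prevails. What happens after that stop is not stated.

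Finally, does another section supply the missing rule?
- 4.7 covers withdrawal from the study.
- 11.2.1 lets the investigator interrupt administration for adverse events.
- 11.6 lets an infusion be ended at any time and points back to 5.3.
- 11.7 pauses enrolment.
- 11.8 decides whether the next dose level opens.

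None of these says whether an infusion stopped under the absolute criteria may be restarted.

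**The case against.** The strongest reply is that the text already works. The contrast wording makes the stop prevail, so the discretionary entry for these two signs is merely redundant. Suspected anaphylaxis is an absolute stop in its own right. The investigator or sponsor can end any infusion at any time. Section 6.3.6 provides for emergency medication, resuscitation equipment and trained staff. All of this stands, and it narrows the point considerably. It does not remove the duplicate entry, and it does not say whether an absolute stop is final.

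A reader might infer more than the document supports, in three ways.

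- *That 5.3 permits restart after an absolute stop.* It does not. The resumption sentences come before the absolute list and attach to the first list. Restart after an absolute stop is unaddressed, and the contrast wording suggests that a permanent stop was intended.
- *That 5.3 conflicts with 11.8, where a single immediate hypersensitivity event bars the next dose level.* The two rules act at different levels: one governs a single infusion, the other the opening of a cohort. Such an event would count under 11.8 whether or not the infusion was restarted, and ungraded breathlessness is not by itself such an event.
- *That the undelivered dose measures the defect.* Most of the dose does remain early in an infusion, but that is true of an interruption for any reason. The document gives no probability of wheeze or dyspnoea from which to derive an expected effect.

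The antitoxin comparison also has limits: 8.1.1 expects a lower risk with SAB-176 because it is human IgG.

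**Conclusion.** The point holds as a drafting fault in a real-time safety rule. Two of the six repeated signs have two instructions, and finality after an absolute stop is left unstated. Given the safeguards already in place, the residual risk is isolated wheeze or dyspnoea that nobody has yet labelled anaphylaxis. The fault should be corrected because the product is flagged for hypersensitivity and the correction is short. It does not touch sample size, endpoints or the escalation criteria.

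The conclusion rests on two readings: that the contrast wording gives the absolute list precedence, and that the saturation qualifiers do not extend to shortness of breath and wheezing. Both follow the ordinary sense of the text. The frequency of such events is unknown, so no numerical size is offered.

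**What to change.** Make two edits in 5.3. First, remove shortness of breath and wheezing from the discretionary list, leaving desaturation that does not reach the absolute threshold. Second, add a sentence after the absolute list: an infusion stopped under these criteria is not resumed. If the sponsor wants to be able to manage mild, transient breathlessness, the alternative to the first edit is to give the two signs a severity grade in the absolute list, so that they step up like the other four. Either way, each sign then has one instruction.

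The cost is partial dosing. The added sentence covers every absolute criterion on either arm, including a brief saturation below 92% or a transient systolic pressure below 85 mmHg. To illustrate, suppose the stop comes at 15 or 30 minutes (assumed times). The rate starts at 0.5 mL/kg/hr, "escalating by 0.5 mL/kg/hr increments every 15 minutes". The volume given is 0.5 × 0.25 = 0.125 mL/kg at 15 minutes and 0.125 + 1.0 × 0.25 = 0.375 mL/kg at 30 minutes. Multiplying by the Table 3 concentration and dividing by the dose gives:

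| Cohort | Concentration (mg/mL) | Dose (mg/kg) | Given by 15 min | Given by 30 min |
|---|---|---|---|---|
| 1 | 1 | 1 | 12.5% | 37.5% |
| 2 | 4 | 10 | 5% | 15% |
| 3 | 20 | 25 | 10% | 30% |
| 4 | 20 | 50 | 5% | 15% |

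One such SAB-176 subject is 1 of 2, 4, 6 or 8 active subjects in cohorts 1 to 4, and would not contribute PK data at the planned dose. That is a real loss in the small cohorts, but an acceptable one for a first study whose primary objective is safety.

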5.4 Justification of Dose

The proposed starting dose for this Phase 1 study is 1 mg/kg administered as a single IV infusion. Based on the non-clinical toxicology results in New Zealand white rabbits, the no observed adverse effect level was considered to be 725.30 mg/kg/day or higher. The 725.30 mg/kg dose was the maximum dose available to test due to dose volume limitations for the species. Using body surface area calculations (5) and 5X safety factor, a 50 mg/kg dose (The maximum therapeutic target dose for SAB-176) is equivalent to 770.8 mg/kg in rabbits. The planned 1 mg/kg starting dose for humans is approximately 47X lower than the maximum recommended starting dose.

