3.2 Study Design

This safety and tolerability study of intravenous (IV) SAB-176 consists of up to 4 single dose-levels or cohorts (cohort 1–4) in a double-blind, randomized, placebo-controlled dose-escalating cohort design. Four cohorts of 2–10 subjects each will be administered a single IV dose of SAB-176 or saline placebo. At very low doses, the concern is primarily allergic or T-cell activation/cytokine storm, so small cohort sizes should be utilized. As the target dose is approached, the sample size will increase to increase the likelihood of detecting toxicity events. The cohorts and dose levels are outlined in [Table 1](#).

Table 1: Cohorts and Dose Levels

Cohort	Number of Subjects Receiving SAB-176				Number of Subjects Receiving Saline Control
	1 mg/kg	10 mg/kg	25 mg/kg	50 mg/kg	
1	2				1
2		4			2
3			6		2
4				8	2

The number of subjects dosed will follow the limitations below:

- The first three subjects of each cohort will be dosed every other day (48-hour interval).
- For Cohorts 2–4, 48 hours after the third subject is dosed, up to 3 subjects may be dosed per day, until the cohort is completed, and no more than 8 subjects will be dosed per week.
- For cohorts 2, 3, and 4, additional dosing in the cohort may continue only after the safety committee recommends continuation after reviewing the safety data from the 3 initial subjects of the cohort.
- After the first three in each cohort, subsequent subjects will be observed for at least 4 hours before beginning the next infusion in the next subject.

Table 2. Example of dosing timeline

	Infusion Day								
	1	2	3	4	5	6	7	8	9
Subject 1	X								
Subject 2			X						
Subject 3					X				
Subject 4							X*		

Table 2. Example of dosing timeline (con't)

	Infusion Day								
	1	2	3	4	5	6	7	8	9
Subject 5							X (≥4 hrs post Subject 4)		
Subject 6							X (≥4 hrs post Subject 5)		
Subject 7								X	
Subject 8								X (≥4 hrs post Subject 7)	
Subject 9								X (≥4 hrs post Subject 8)	
Subject 10									X

* Additional enrollment in the cohort may continue only after the safety committee recommends continuation after reviewing the safety data from the three initial subjects of the cohort.

NOTE: Only 1 subject should be infused at any given time. An infused subject should be observed for at least four hours prior to beginning the next infusion.

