8 RISKS AND BENEFITS

8.1 Potential Risks

8.1.1 Risks of SAB-176

The risks of SAB-176 are largely unknown. However, a previous Phase 1 study of SAB-301 (anti-Middle Eastern Respiratory Syndrome virus immunoglobulin) derived from Tc bovines was shown to be safe and well tolerated at the highest dose of 50 mg/kg proposed in this study. It is anticipated that the risks will be similar to SAB-301 and human derived IVIg with some unique considerations for proteins of animal origin as discussed below.

Based on human IVIg, common side effects may include:

- Headache
- Injection site reaction
- Nausea
- Urticaria
- Fatigue
- Arthralgia
- Pyrexia

Less common side effects may include:

- Vomiting
- Back pain
- Rash

Serious side effects seen with human IVIg that could be seen with SAB-176 include:

- Hyperproteinemia, with resultant changes in serum viscosity and electrolyte imbalances may occur in patients receiving IVIg therapy (6). Humans routinely receive up to 1-2 grams/kg of human-derived IVIg to treat Guillain-Barre syndrome and other immune related neuropathies. Therefore, the addition of 50 mg/kg IgG as SAB-176 is a relatively

small amount and is unlikely to cause AEs related to increased viscosity.

- Aseptic Meningitis Syndrome (AMS) has been reported with IVIg treatments, especially with high doses or rapid infusion. This risk is anticipated to be minimized given the low amount of protein and relatively slow infusion.
- Hemolysis, either intravascular or due to enhanced RBC sequestration, can be seen with human IVIG. This risk is anticipated to be low given the lack of exposure of the cows to human RBC antigens.
- Volume overload has been reported with human IVIg. This risk is anticipated to be minimized given the low amount of protein and small total volumes administered.

There may be unique risks given the animal origin of the IVIg. SAB-176 is a human IgG so it is anticipated the risk with SAB-176 would be less, though there may be residual animal proteins. The most similar product would be an animal polyclonal antibodies to non-human proteins e.g. Horse Heptavalent Botulism Antitoxin.

(<http://www.fda.gov/downloads/BiologicsBloodVaccines/BloodBloodProducts/ApprovedProducts/LicensedProductsBLAs/FractionatedPlasmaProducts/UCM345147.pdf>)

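### Do the 770.8 mg/kg rabbit figure in Section 5.4 and two rate proportions in Table 3 undermine the dose justification?

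*Protocol*

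**What the plan says.** Section 5.4 of the protocol reports that in rabbits "the no observed adverse effect level was considered to be 725.30 mg/kg/day or higher", and adds: "The 725.30 mg/kg dose was the maximum dose available to test due to dose volume limitations for the species". It then names body-surface scaling and a 5X safety factor and states that "a 50 mg/kg dose (The maximum therapeutic target dose for SAB-176) is equivalent to 770.8 mg/kg in rabbits". The 1 mg/kg starting dose is described as "approximately 47X lower than the maximum recommended starting dose".

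Section 5.3 gives the comparator for infusion speed: 10% human immunoglobulin, started at 0.6 mL/kg/hr, where "the rate can be increased gradually to a maximum of 4.8 mL/kg/hr". Table 3 expresses each cohort's start and end rate as a proportion of that comparator. For Cohort 3 it prints 1/6 to 1/12, and for Cohort 4 it prints 1/6 to 1/10.

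Section 8.1.1 reports that a related product from the same animal platform was "shown to be safe and well tolerated at the highest dose of 50 mg/kg proposed in this study". On aseptic meningitis it says: "This risk is anticipated to be minimized given the low amount of protein and relatively slow infusion".

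**The concern.** Read quickly, Section 5.4 places a rabbit equivalent of 770.8 mg/kg for the top dose directly after a highest tested dose of 725.30 mg/kg. If 770.8 were a plain equivalent, the animal study would not have covered the 50 mg/kg exposure at all. If it already contains the 5X factor, a full fivefold margin was not shown, and the text does not say so. This is the protocol's only quantitative nonclinical statement about the top dose, which eight subjects are due to receive (Table 1), so a reader should be able to tell which reading applies.

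The Table 3 proportions raise a smaller doubt. If two of them disagree with the printed rates, one may ask whether the proportions or the rates are wrong. The rates are what the site will run, and Section 8.1.1 leans on the infusion being slow.

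**Working it through.** **Inputs.** Section 5.4: 725.30 mg/kg, 770.8 mg/kg, 50 mg/kg, 5X, 1 mg/kg, 47X. Section 5.3: comparator 10 g/100 mL = 100 mg/mL, at 0.6 and 4.8 mL/kg/hr. Table 3: dose, concentration, rates, proportions and durations. The rabbit-to-human conversion k is not printed, so it is solved from the protocol's own figures.

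**Which reading of 770.8 fits?**

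- With the 5X inside: k = 770.8 / (50 × 5) = 3.083. The maximum recommended starting dose is then 725.30 / 3.083 / 5 = 47.05 mg/kg, which is 47 times the 1 mg/kg start. The plan's 47X is reproduced.
- Without the 5X: k = 770.8 / 50 = 15.4. The maximum recommended starting dose would be 725.30 / 15.416 / 5 = 9.4 mg/kg, which contradicts 47X.

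So 770.8 is the product of the plain equivalent and the safety factor. The plain equivalent of 50 mg/kg is 50 × 3.083 = 154.2 mg/kg.

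**Margin at 50 mg/kg.** 725.30 / 154.2 = 4.70. Equivalently, 5 × 725.30 / 770.8 = 4.70, which needs no value of k. If k is varied from 3.08 to 3.10, the margin runs from 725.30 / 154.0 = 4.71 to 725.30 / 155.0 = 4.68. The tested dose is 1 − 725.30 / 770.8 = 5.9% below the multiplied figure; put the other way, 770.8 is 6.3% above it. Because the no-effect level is given as that dose or higher, 4.7 is a lower bound.

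**Table 3 proportions.** The comparator is 0.6 × 100 = 60 mg/kg/hr at the start and 4.8 × 100 = 480 mg/kg/hr at the maximum.

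| Cohort | Start / 60 | Printed | End / 480 | Printed |
|---|---|---|---|---|
| 1 | 0.5/60 = 1/120 | 1/120 | 2/480 = 1/240 | 1/240 |
| 2 | 2/60 = 1/30 | 1/30 | 12/480 = 1/40 | 1/40 |
| 3 | 10/60 = 1/6 | 1/6 | 20/480 = 1/24 | 1/12 |
| 4 | 10/60 = 1/6 | 1/6 | 40/480 = 1/12 | 1/10 |

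Six of eight entries reproduce exactly, so the method is clear and two entries are slips.

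**Are the rates for Cohorts 3 and 4 themselves in doubt?** Use Section 5.3's steps of 0.5 mL/kg/hr every 15 minutes.

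- Cohort 3: volume 25/20 = 1.25 mL/kg. The first 15 min at 0.5 deliver 0.125. The remaining 1.125 at 1 mL/kg/hr takes 67.5 min. Total 82.5 min, printed 83.
- Cohort 4: volume 50/20 = 2.5 mL/kg. Three steps (0.125 + 0.25 + 0.375 = 0.75) take 45 min. The remaining 1.75 at 2 mL/kg/hr takes 52.5 min. Total 97.5 min, printed 97.

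Concentration times mL/kg/hr also returns the printed mg/kg/hr rates (20 × 1 = 20 and 20 × 2 = 40). For these two cohorts the rate and duration columns support each other, and only the two end proportions stand apart.

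**The case for a change.** The case for a correction is that a dose-justification section should be reproducible by an ethics committee or safety committee without back-solving. The word equivalent is loose when the number is five times the equivalent. The text sets 725.30 and 770.8 in neighbouring sentences without saying that the second was not reached, and a reader may infer that a fivefold margin was met. Two table entries are plainly wrong, by factors of 2 and 1.2, and correcting text costs almost nothing.

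The arithmetic in that case stands in full, and so does the criticism of the wording. What does not stand is that anything in the plan rests on it. The 5X factor is disclosed in the sentence that contains 770.8. The section nowhere says that the margin at 50 mg/kg is five, so there is no false statement to withdraw. The volume limit on the rabbit dose is stated openly, and both figures are there to compare. The 47 mg/kg that the figures imply is a reference for a starting dose, which 1 mg/kg meets; it is not a ceiling on escalation. Reaching 50 mg/kg depends on staggered dosing and committee review within cohorts (Section 3.2) and on observed events (Section 11.8), none of which uses the animal margin. Section 8.1.1 also cites human experience at that dose with a related product, although this does not supply an animal margin.

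On Table 3, both slips overstate speed relative to immunoglobulin. With the recomputed values, the statement about slow infusion in Section 8.1.1 is better supported, not worse.

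**Conclusion.** No change to the plan follows. Section 5.4 is loosely worded but arithmetically coherent: its figures agree on a conversion of about 3.083, with 770.8 mg/kg being five times a plain equivalent of about 154.2 mg/kg. The margin shown at 50 mg/kg is at least 4.7 (4.68 to 4.71 over conversions of 3.10 to 3.08), and the protocol asserts no larger one. The two Table 3 end proportions (1/12 and 1/10 printed, 1/24 and 1/12 recomputed) are clerical and descriptive; the rates and durations for those cohorts agree with each other.

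This rests on 770.8 containing the 5X factor, which the 47X figure confirms, and on the comparator rates printed in Section 5.3. It is not a judgement on whether any dose or rate is appropriate. The wording and the two entries can be reconciled if these sections are reopened for another reason, but no dose, infusion rate, escalation decision, endpoint or analysis would differ.
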